12.1.6. Electrocardiogram

A 12-lead ECG will be obtained after 5 to 15 minutes of rest in the supine position using equipment at the site and according to the schedule in Appendix 1. The Investigator or designee will evaluate the ECG for abnormalities.

12.1.7. Laboratory Assessments

Clinically significant abnormal laboratory findings identified during the screening period should be recorded as medical history in the CRF.

Laboratory samples will be collected according to the schedules in Appendix 1.

Clinically significant abnormal laboratory test results should be followed until a return to normal or baseline values.

Details for the collection, processing, storage, and shipment of samples can be found in the study laboratory manual.

12.1.7.1. Hematology

Hematology tests will include RBC count, white blood cell (WBC) count, hemoglobin (Hgb), hematocrit (HCT), WBC differential count (neutrophils, lymphocytes, eosinophils, monocytes, and basophils), mean corpuscular hemoglobin concentration (MCHC), mean corpuscular hemoglobin (MCH), mean corpuscular volume (MCV), mean platelet volume (MPV), red blood cell distribution width (RDW), platelet count (Plt), and reticulocyte count (retic).

12.1.7.2. Blood Chemistry

Blood chemistry tests will include sodium (Na), potassium (K), magnesium (Mg), chloride (Cl), bicarbonate (CO2), calcium (Ca), phosphate (PO4), blood urea nitrogen (BUN), creatinine, total protein, glucose, lactate dehydrogenase (LDH) (Week 1 only), aspartate aminotransferase (AST), alanine aminotransferase (ALT), alkaline phosphatase (ALP), total bilirubin (TBILI), and albumin.

12.1.7.3. Iron Panel

Blood samples will be collected for an iron panel to include: iron (Fe), ferritin, transferrin saturation, and total iron binding capacity.

12.1.7.4. Prothrombin Time, Activated Partial Thromboplastin Time, and International Normalized Ratio

Blood samples collected during screening will be used to determine prothrombin time (PT), activated partial thromboplastin time (aPTT), and international normalized ratio (INR) to assess coagulation.

12.1.7.5. Urinalysis

Urinalysis will include appearance, glucose, ketones, blood, protein, nitrite, bilirubin, specific gravity, pH, urobilinogen, and leukocytes. If the results are positive for blood or protein, a microscopic examination should be included.

12.1.7.6. Pregnancy Screen

A serum pregnancy test must be performed within 7 days before the first study drug administration. A urine pregnancy test will be performed according to the schedule in Appendix 1.

12.1.7.7. Male Fertility Analysis

Fertility tests for male patients will include orchidometry, semen analysis, and measurement of testosterone, follicle-stimulating hormone, luteinizing hormone, and inhibin B levels, according to the Schedule of Events, Appendix 1. Male patients must be provided with information about the option for sperm banking before providing written informed consent.

12.2. Adverse and Serious Adverse Events

12.2.1. Definition of Adverse Events

12.2.1.1. Adverse Events

An AE is defined as any untoward medical occurrence in a patient regardless of its causal relationship to study treatment. An AE can be any unfavorable and unintended sign (including any clinically significant abnormal laboratory test result), symptom, or disease temporally associated with the use of the study drug, whether or not it is considered to be study drug related. Included in this definition are any newly occurring events and any previous condition that has increased in severity or frequency since the administration of study drug. Disease progression is a study endpoint and consequently, should not be reported as an AE. However, if a patient dies from disease progression with no other immediate causes, "disease progression" should be reported as an SAE (Section 12.7).

All AEs that are observed or reported by the patient during the study (from the time of administration of the first dose of study drug until the final visit indicated in Appendix 1) must be reported, regardless of their relationship to study drug or their clinical significance.

12.2.1.2. Serious Adverse Events

An SAE is any AE occurring at any dose and regardless of causality that meets any of the following criteria.

- Results in death
- Is life-threatening
- Requires inpatient hospitalization > 24 hours or prolongation of existing hospitalization
- Results in persistent or significant incapacity or substantial disruption of the ability to conduct normal life functions
- Is a congenital anomaly or birth defect in an offspring of a patient taking study drug
- Is an important medical event

The term "life-threatening" refers to an event in which the patient is at immediate risk of death at the time of the event. The term does not refer to an event that hypothetically might cause death if it were more severe.

Important medical events are those that may not meet any of the criteria defined above; however, they may be considered serious when, based upon appropriate medical judgment, they may jeopardize the patient and may require medical or surgical intervention to prevent one of the other outcomes listed in the SAE definition.

Pregnancy is not considered an AE; however, information will be collected for any pregnancies that occur during the study (from the time the first dose of study drug is administered until the final visit indicated in Appendix 1). Certain pregnancy outcomes will require submission as an SAE.

The Investigator is responsible for reporting to Peloton Therapeutics or designee all AEs and SAEs that are observed or reported by the patient during the study (from the time the first dose of study drug is administered until the final visit indicated in Appendix 1), regardless of their relationship to study drug or their clinical significance. All SAEs reported or observed during the study must be followed to resolution or until the Investigator deems the event to be chronic or the patient to be stable. Peloton Therapeutics or designee may contact the Investigator to obtain additional information on any SAE that has not resolved at the time the patient completes the study.

12.3. Eliciting Adverse Event Information

At every study visit, patients must be asked a standard, non-directed question, such as, "How do you feel?" or "How have you been feeling since your last visit?" to elicit any medically related changes in their well-being. They may also be asked if they have been hospitalized, had any accidents, used any new medications, or changed concomitant medication regimens (including prescription drugs, over-the-counter medications, vitamins, herbal products, and minerals). Responses should be recorded in the source documents.

In addition to patient observations, AEs must be documented for any clinically significant diagnosis resulting from abnormal laboratory test values, physical examination findings, or ECG abnormalities, or from other documents that are relevant to patient safety.

12.4. Assessment of Causality

The Investigator must use the following classifications and criteria to characterize the relationship or association of PT2385 in causing or contributing to the AE:

Unrelated: This relationship suggests that there is no association between the study drug and the reported event.

Unlikely: This relationship suggests that the temporal sequence of the event with study drug administration makes a causal relationship improbable and/or other factors also provide plausible explanations.

Possible: This relationship suggests that treatment with the study drug caused or contributed to the AE. That is, the event follows a reasonable temporal sequence from the time of study drug administration, and/or, follows a known response pattern to the study drug, but could have been produced by other factors.

Probable: This relationship suggests that a reasonable temporal sequence of the event with study drug administration exists and, based upon the known pharmacological action of the drug, known or previously reported adverse reactions to the drug or class of drugs, or judgment based on the Investigator's clinical experience, the association of the event with study drug administration seems likely.

12.5. Assessment of Severity

The Investigator will grade the severity of the AEs as Grades 1, 2, 3, 4, or 5 based on NCI CTCAE 4.03 or subsequent versions released during the study. If the CTCAE do not apply, severity should be defined as shown in Table 3.

Grade	Description
1	Mild; asymptomatic or mild symptoms; clinical or diagnostic observations only; intervention not indicated.
2	Moderate; minimal, local or noninvasive intervention indicated; limiting age-appropriate instrumental activities of daily living.
3	Severe or medically significant but not immediately life-threatening; hospitalization or prolongation of hospitalization indicated; disabling; limiting self-care activities of daily living.
4	Life-threatening consequences; urgent intervention indicated.
5	Death related to AE.

Table 3Adverse Event Severity Grades

The NCI CTCAE 4.03 will be provided to the Investigator.

12.6. Recording Adverse Events

All conditions present before administration of the first dose of study drug should be documented as medical history. All drug-related (possible or probable, see Section 12.4) AEs and abnormal laboratory test results reported or observed during the study must be followed to resolution (either return to baseline or within normal limits). All other AEs will be followed through the final visit indicated in Appendix 1. Information to be collected includes type of event, date of onset, date of resolution, Investigator-specified assessment of severity and relationship to study drug, seriousness, as well as any action taken.

While an AE is ongoing, changes in the severity (e.g., worsening and improving) should be noted in the source documents but, when documenting the AE, only the total duration and greatest severity should be recorded in the CRF. AEs characterized as intermittent require documentation of onset and duration.

AEs resulting from concurrent illnesses, reactions to concurrent illnesses, reactions to concurrent medications, or progression of disease states must also be reported. Preexisting conditions (present before the start of the AE collection period) are considered concurrent medical conditions and should NOT be recorded as AEs. However, if the patient experiences a worsening or complication of such a concurrent condition, the worsening or complication (except disease progression) should be recorded as an AE. Investigators should ensure that the AE term recorded captures the change in the condition (e.g., "worsening of...").

Each AE should be recorded to represent a single diagnosis. Accompanying signs (including abnormal laboratory test values or ECG findings) or symptoms should NOT be recorded as additional AEs. If a diagnosis is unknown, sign(s) or symptom(s) should be recorded as an AE(s). Changes in laboratory test values or ECG parameters are only considered to be AEs if they are judged to be clinically significant (i.e., if some action or intervention is required or if the Investigator judges the change to be beyond the range of normal physiologic fluctuation). If abnormal laboratory test values or ECG findings are the result of pathology for which there is an overall diagnosis (e.g., increased creatinine levels in renal failure), only the diagnosis should be reported as an AE.

Elective procedures (surgeries or therapies) that were scheduled before the start of AE collection are not considered AEs. These elective procedures should not be recorded as AEs, but should be documented in the patient's source documents as elective (e.g., elective periodontal surgery). However, if a pre-planned procedure is performed early (e.g., as an emergency) because of a worsening of the preexisting condition, the worsening of the condition should be captured as an AE.

12.7. Reporting Serious Adverse Events

Any AE that meets the previously described criteria for "serious" must be reported to the Sponsor's designee within 24 hours from the time when site personnel first learn about the event. To report the SAE, fax or email the completed SAE form to SCRI Development Innovations Pharmacovigilance Department (contact information listed in Table 4) within 24 hours of awareness. For questions regarding SAE reporting, SCRI Development Innovations Safety personnel can be contacted by phone, fax or email, see Table 4.

Table 4Serious Adverse Event Reporting Contact Information

The Investigator must continue to follow the patient until the SAE has subsided or until the condition becomes chronic in nature, stabilizes (in the case of persistent impairment), or the patient dies. Within 24 hours of receipt of new information, the updated follow-up SAE form, along with any supporting documentation (e.g., patient discharge summary or autopsy reports), should be faxed to SCRI Development Innovations Pharmacovigilance Department (Table 4).

Peloton Therapeutics or designee will notify regulatory agencies of any fatal or life-threatening unexpected events associated with the use of the study drug as soon as possible but no later than 7 calendar days after the initial receipt of the information. Initial notification will be followed by a written report within the timeframe established by the appropriate regulatory agency. For other SAEs that do not meet the fatal or life-threatening unexpected criteria, but are deemed by the Investigator to be associated with the use of the study drug (that is, "possible" or "probable" in causality assessment), Peloton Therapeutics or designee will notify the appropriate regulatory agencies in writing within the timeframe established by those regulatory agencies. Peloton Therapeutics or designee will provide copies of any reports to regulatory agencies regarding serious and unexpected SAEs to the Investigators for their information and submission to their institutional review board (IRB), as appropriate.

Principal Investigators are responsible for informing their IRB of any SAEs at their site, as appropriate. Serious AE correspondence with regulatory authorities or IRBs must be submitted to Peloton Therapeutics or designee for recording in the study file.

12.8. Pregnancy

Female patients of child-bearing potential are defined as patients who are not surgically sterile (no history of bilateral tubal ligation, hysterectomy, or bilateral salpingo-oophorectomy), do not have fallopian inserts with confirmed blockage, have not had reproductive potential terminated by radiation, and have not been postmenopausal for at least 1 year.

12.8.1. Methods of Birth Control

During screening, while taking study drug, and until 30 days after taking the final dose of study drug, female patients of child-bearing potential and male patients who have female partners of child-bearing potential (defined as all women physiologically capable of becoming pregnant) must practice one of the following methods of birth control:

- Total abstinence,
- Male or female sterilization, or
- Combination of any 2 of the following (a + b or a + c or b + c):
 - a. Use of oral, injected or implanted hormonal methods of contraception
 - b. Placement of an intrauterine device (IUD) or intrauterine system (IUS)
 - c. Barrier methods of contraception: condom or occlusive cap (diaphragm or cervical/vault caps) with spermicidal foam/gel/film/cream/vaginal suppository

12.8.2. Suspected Pregnancy

During the study, all females of child-bearing potential must be instructed to contact the Investigator immediately if they suspect they might be pregnant (e.g., late or missed menstrual period). Male patients must be instructed to contact the Investigator if a sexual partner suspects she may be pregnant.

If a patient or Investigator suspects that the patient may be pregnant, study drug administration must be held until the results of a serum pregnancy test are available. If pregnancy is confirmed, the patient must discontinue taking study drug. The Investigator must immediately report a pregnancy associated with study drug exposure and record the event. The protocol-required early termination procedures noted in Appendix 1 must be performed. Other appropriate follow-up procedures should be considered if indicated.

Pregnancy is not considered an AE; however, the Investigator must follow a pregnant patient, or the pregnant female partner of a male patient (if consenting), and report follow-up information regarding the course of the pregnancy, including perinatal and neonatal outcome. Infants resulting from such pregnancies should be followed for a minimum of 8 weeks. Peloton Therapeutics or designee may contact the Investigator to request additional information throughout the course of the pregnancy.

The following post-pregnancy outcomes must be considered SAEs and will require additional reporting in the CRF and on an SAE form.

- Congenital anomaly/birth defect
- Stillbirth
- Spontaneous miscarriage

13. STATISTICS

This section describes the statistical methodology to be used in the analysis of protocol endpoints. These methods will be documented in a formal statistical analysis plan (SAP) detailing the analyses to be performed, which will be developed before the final database lock. The SAP will serve as the final arbiter of all statistical analyses. The SAP will describe the analysis of all safety, efficacy, PK, and PD response variables. Any changes to the methodology described in the final approved SAP will be presented and discussed in the clinical study report.

13.1. Determination of Sample Size

This study will be conducted with a 2-stage design (Green and Dahlberg, 1992) which allows for an early assessment of futility. If after the first 25 patients have been enrolled to the study, 2 or fewer patients have had a confirmed response, further enrollment will be temporarily suspended for up to a year or until at least 3 responses are seen; if 3 responses are not seen within 1 year after enrollment of the 25th patient, no further patients will be enrolled and the study will be discontinued. In addition, if more than 2 of the first 6 patients enrolled experience treatment-limiting toxicity during the first 4 weeks of their treatment, the protocol will be modified or the study will be stopped. If 3 or more of the 25 patients respond, enrollment will proceed to the second stage of the design.

A total of 25 patients will be enrolled into the second stage of the study for a total required enrollment of 50 patients. If at least 13 of the 50 patients (25 + 25) respond (CR or PR), then the hypothesis that PT2385 is ineffective will be rejected.

The required sample size for this 2-stage design is based on the following design parameters: The null hypothesis is that PT2385 is ineffective, defined as an ORR (best confirmed response of PR or CR) of 15% (P_0 =0.15). The alternative hypothesis is that PT2385 is effective, defined as an ORR of 30% (P_1 =0.3). The probability of falsely concluding that the agent is effective when it is truly ineffective is 0.05 (alpha) and the probability of falsely concluding that the agent is ineffective when it is truly effective is 0.2 (beta).

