be summarized. Estimates of the ccRCC ORR along with the associated 90% and 95% exact binomial confidence intervals (Clopper-Pearson method) will be provided. The binomial probability that the observed ccRCC ORR is > 0.15 will be calculated. Best confirmed response will be summarized. The ccRCC TTR will be calculated for patients who achieve a ccRCC CR or PR. The maximum percent decrease in ccRCC tumor burden will be displayed using waterfall plots. The ccRCC PFS and ccRCC DOR will be summarized descriptively using the Kaplan-Meier method. The median and quartiles of ccRCC PFS and ccRCC DOR will be calculated along with 90% and 95% confidence intervals.

Summaries of the response endpoints will also be provided for subgroups of the Efficacy Analysis Set as follows: Subgroups will be defined based on site of primary tumors other than ccRCC at screening, blood level of PT2385 based on the PK assessments, and duration of PT2385 treatment. The analyses of ORR, PFS, best confirmed response, and DOR will be performed in each of these subgroups.

The ORR, PFS, DOR, and TTR will be summarized for the individual types of non-ccRCC tumors using modified RECIST 1.1 criteria. The modification to RECIST 1.1 is to evaluate different organ system tumors independently (e.g., VHL disease-associated solid tumors in the pancreas, adrenal gland, or hemangioblastomas or retinal angiomas).

The determination of response and progression will be made by the local investigators. The investigator assessments will be used for decisions regarding treatment for individual patients and by the DMC for approval to open Stage 2 of the study. The response outcomes will also be reviewed and determined by an Independent Review Committee (IRC). For the primary analysis of ORR, the determination of response will be based on independent radiologic assessment conducted by the IRC. Both the investigators' and the IRC's assessments will be used for the summaries and analyses of efficacy.

Safety Assessments

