13.3. Statistical Analyses

All statistical summaries and analyses will be performed in SAS® Version 9.1 or higher (SAS Institute Inc., Cary, NC, USA) on a PC platform.

Results will be reported using summary tables, figures, and data listings. No inferential statistical analyses will be performed. For continuous variables, the number of patients with non missing data (n), mean, standard deviation, median, minimum, and maximum will be presented. For discrete data, the frequency and percent distribution will be presented. Unless otherwise indicated, percentages will be calculated based upon the number of patients in the Safety Analysis Set as the denominator. Graphical methods will be used, as appropriate, to illustrate study endpoints.

Summaries will be provided for the total number of patients in the population of interest and for selected variables, and subsets of patients in the population of interest.

Data recorded on the electronic case report forms and any derived data will be presented by patient in data listings.

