13.3.4. Efficacy Analyses

The primary summaries of all response data will be based on the Efficacy Analysis Set.

Response of ccRCC tumors will be measured by contrast enhanced computerized tomography (CT) or magnetic resonance image (MRI) scan and assessed according to RECIST 1.1, modified to follow ccRCC tumors only.

Response assessments of ccRCC CR and PR should be confirmed by a second assessment. Where confirmed responses are required, the date of the first assessment will be used in all analyses. In the case that the confirmation assessment is not available, the assessment at the next scheduled time point will be used for confirmation. If there are no assessments, the response will be taken to be unconfirmed and a non response.

The ccRCC ORR is defined as the proportion of patients for whom the best confirmed ccRCC response is CR or PR, determined by RECIST 1.1. Estimates of the ccRCC ORR along with the associated 90% and 95% exact binomial confidence intervals (Clopper Pearson) will be provided. The binomial probability that the observed ccRCC ORR is > 0.15 will be calculated. Best confirmed ccRCC response will be summarized.

The ccRCC PFS is defined the interval from the start of study treatment until the earlier of the first documentation of ccRCC disease progression determined by RECIST 1.1 or death from any cause, whichever occurs first. Renal cell carcinoma PFS will be right censored for patients who meet one of the following conditions: 1) no post baseline disease assessments, 2) non protocol systemic anticancer treatment started before documentation of disease progression or death, 3) surgery that is considered to affect response before documentation of disease assessment visit, 5) alive and does not have documentation of disease progression before a data analysis cutoff date. The Kaplan-Meier (KM) method will be used to estimate the distribution of ccRCC PFS. Quartiles including the median will be estimated by KM method along with their 95% confidence intervals. A figure showing the estimated ccRCC PFS distribution will be provided. KM cumulative estimators along with the associated 95% CIs will be provided for ccRCC PFS rates at 26, 39 and 52 weeks. Duration of follow up for ccRCC PFS will be summarized according to the KM estimate of potential follow up also termed "reverse Kaplan-Meier."

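### The stated false-negative probability of 0.2 at a true ORR of 30% is not met: the 25+25 design with the 13-of-50 rule has an exact beta of 0.224 (power 77.6%)

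*Combined protocol and SAP*

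**What the plan says.** Section 13.1, repeated in the synopsis under sample size determination, describes the design as follows: "This study will be conducted with a 2-stage design (Green and Dahlberg, 1992) which allows for an early assessment of futility".

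- **Stage 1.** 25 patients. The futility condition is "If after the first 25 patients have been enrolled to the study, 2 or fewer patients have had a confirmed response"; accrual is then suspended for up to a year, and the study stops if a third response does not appear. Otherwise, "If 3 or more of the 25 patients respond, enrollment will proceed to the second stage of the design".
- **Final rule.** 25 more patients are enrolled. "If at least 13 of the 50 patients (25 + 25) respond (CR or PR"), the hypothesis of ineffectiveness is rejected.
- **Parameters.** The null ORR is 15%, the alternative ORR is 30% and alpha is 0.05. For the other error rate, "the probability of falsely concluding that the agent is ineffective when it is truly effective is 0.2 (beta").

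Neither section gives the error rates that the rule actually attains, and neither says whether alpha is one-sided.

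Three sentences elsewhere bear on the same test:

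- The synopsis says "The binomial probability that the observed ccRCC ORR is > 0.15 will be calculated", and Section 13.3.4 repeats this.
- Section 13.3.4 plans the ORR estimate with "associated 90% and 95% exact binomial confidence intervals".
- Section 13.3 says "No inferential statistical analyses will be performed".

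**The concern.** The stage sizes, the gate, the final cut-off and both response rates are all given, so the two error rates follow from them and can be checked. When a sample size is presented as the one required for a beta of 0.2, that figure works as an upper limit. A reader of Section 13.1 will conclude that a drug with a true ORR of 30% has an 80% chance of being declared effective.

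If the rule does not deliver that, the risk of discarding a useful drug is understated. What is at stake is the accuracy of the reported power. The risk of wrongly declaring an ineffective drug effective is a separate matter and is checked alongside.

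**Working it through.** **Inputs, all from Section 13.1:** stage sizes n1 = 25 and n2 = 25; continue if X1 ≥ 3; reject if X1 + X2 ≥ 13; p0 = 0.15; p1 = 0.30; stated alpha 0.05 and beta 0.2. Assumptions: all 50 patients are dosed and counted (no dropout allowance is given), and the same response assessment is used at the gate and at the end.

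**Step 1. Exact two-stage calculation.**

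P(reject | p) = Σ over x = 3,…,25 of P(X1 = x | 25, p) × P(X2 ≥ 13 − x | 25, p)

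- At p = 0.15: 0.02997, so the attained one-sided alpha is 0.030.
- At p = 0.30: 0.77635, so power is 77.6% and beta = 1 − 0.77635 = 0.22365.

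The stated beta of 0.2 is not reproduced. The gap is 0.22365 − 0.20 = 0.02365, or 2.4 percentage points. In relative terms the miss rate is 0.02365 / 0.20 ≈ 12% higher than stated.

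**Step 2. Is the futility gate responsible?** Drop it and use a single binomial with 50 patients:

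- P(X ≥ 13 | 50, 0.15) = 0.03006
- P(X ≥ 13 | 50, 0.30) = 0.77713

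The gate costs 0.77713 − 0.77635 = 0.0008 of power. At a true ORR of 30% only 0.9% of studies would have 2 or fewer responders among the first 25. A gate can only lower power, so no reading of the interim rule, including the one-year suspension, takes the 13-of-50 rule above 77.7%.

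**Step 3. Would another cut-off at 50 patients work?** With the same gate:

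| Reject if at least | Alpha at 15% | Power at 30% |
|---|---|---|
| 12 of 50 | 0.062 | 85.9% |
| 13 of 50 | 0.030 | 77.6% |
| 14 of 50 | 0.013 | 67.2% |

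Thirteen is the smallest cut-off that keeps alpha at or below 0.05. No cut-off at 50 patients satisfies both alpha ≤ 0.05 and beta ≤ 0.2.

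**Step 4. Could an approximation have produced 80%?** A normal approximation to the 13-of-50 rule with continuity correction gives 78.0%. Sample-size formulas at N = 50 give 84.9% (normal, one-sided 0.05), 78.4% (normal, two-sided 0.05) and 82.3% (arcsine, one-sided). Some of these lie near 80%, but the formula figures do not evaluate the rule that the protocol specifies.

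**Step 5. Size in other terms.** Solving the two-stage power for 0.80 gives a true ORR of 30.5%. With the same gate and a cut-off of 13, one more second-stage patient (25 + 26) gives alpha 0.035 and power 80.1%.

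**Step 6. Sidedness.** At exactly 13 of 50 the Clopper-Pearson intervals are 16.1% to 38.1% (90%) and 14.6% to 40.3% (95%). At the decision boundary the 90% interval excludes 15% and the 95% interval does not. The rule therefore agrees with a one-sided 0.05 test, which corresponds to the 90% interval.

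**The case against.** The strongest reply is that the alpha and beta figures are introduced as design parameters. They are targets on which the sample size was based, not claims about what was attained. On that reading, it is inconsistent to accept alpha stated as 0.05 when the rule gives 0.030 while objecting to beta stated as 0.2 when it gives 0.224.

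This lowers the weight of the point but does not remove it. Nominal error rates are upper limits. An alpha of 0.030 respects its limit and a beta of 0.224 exceeds its own, so treating the two differently is justified. The protocol also calls 50 the required enrolment, and 50 patients with this rule do not meet the parameters given.

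A second reply is that 77.6% is itself conditional. Section 13.3.4 uses investigator assessments to open Stage 2 and independent review for the primary ORR, and the efficacy set counts dosed patients, who may not number exactly 50. That is fair, and the assumptions should be stated. A different reader at the gate still cannot raise power above the ungated 77.7% at 50 patients.

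A third reply is that the rule is one-sided on its face and that no sentence ties the decision to a confidence interval. That is also right. Stating the sidedness helps the reader, but its absence leaves the decision rule unambiguous. Likewise, the wording points in Sections 13.3 and 13.3.4 are separate consistency matters and carry none of the arithmetic.

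**Conclusion.** The concern holds as a minor error in the stated power. For the rule as specified, the chance of missing a drug with a true ORR of 30% is 22.4%, not 20%. The result assumes 50 dosed patients and one response assessment at both stages; without any gate the figure would still be 22.3%.

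Type I error is controlled with room to spare, so a positive result is no less secure. The gate and the cut-off need no change.

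The secondary wording is also at odds with the rule. A formal rejection rule cannot coexist with a blanket statement that nothing inferential will be done. And an observed rate either exceeds 15% or does not; the quantity intended must be the tail probability of the observed count under an ORR of 15%.

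**What to change.** Keep 25 + 25, the 3-of-25 gate and the 13-of-50 rule.

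- **Synopsis and Section 13.1.** Replace the alpha and beta sentence with: *One-sided nominal alpha is 0.05 (attained 0.030 at an ORR of 15%); power is 77.6% (beta 0.224) at an ORR of 30%, by exact two-stage binomial calculation assuming 50 dosed patients and the same response assessment at both stages.*
- **Synopsis (efficacy) and Section 13.3.4.** Describe the comparison with 15% as the exact one-sided tail probability P(X ≥ x | n, 0.15), where x is the observed number of responders.
- **Section 13.3.** Limit the exclusion to inferential analyses other than the primary ORR test against 15%.
- **SAP.** Section 13 makes the SAP the final authority on analysis, so carry the same figures and wording there.

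The cost is wording only. The one drawback is that the stated power becomes slightly less favourable. Reaching 80% would need one more second-stage patient (Step 5), but a shortfall of 2.4 points does not call for a design change.
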